2.5.2.3 Part 3 (NOT applicable)

Part 3 of the study aims to further assess the efficacy of the chosen treatment combination from Part 2 by comparing it to ruxolitinib using the FAS.

The comparison of the combination arm to ruxolitinib will be performed separately based on a Bayesian model and include data from both Part 2 and Part 3.

In detail, let n_{rux} and r_{rux} be the sample size and the number of responders with respect to the primary composite endpoint in the ruxolitinib arm, respectively. Analogously, n_{comb} and r_{comb} denote the sample size and the number of responders in the combination arm. The number of responders within each arm is modelled by a binomial distribution with response rate p_i ($i = rux, comb$). As in [Section 2.5.2.2](#), a vague prior, $beta(1/2, 1/2)$, is assumed for p_i . This results in a beta-distributed posterior distribution for the response rate, see [Section 2.5.2.2](#). The study is considered to be successful with respect to the primary endpoint when the difference in response rates between combination arm and ruxolitinib arm is greater than zero with a probability of greater than or equal to 90%:

Figure 2-2 Success criterion for primary endpoint.

$$P(p_{comb} - p_{rux} > 0 | n_{rux}, r_{rux}, n_{comb}, r_{comb}) \geq 0.9$$

The RR will be summarized using descriptive statistics (N, %) by treatment arm along with 95% creditable interval of the RR posterior distribution. The joint distribution of the posterior difference in response rates will be summarized using median and 95% credible interval. The probability that the posterior difference is greater than zero will also be presented.

2.5.3 Handling of missing values/censoring/discontinuations

Subjects with missing assessments of hemoglobin, spleen volume or MF SAF TSS at the end of Week 24 that prevent the evaluation of the primary endpoint will be considered non-responders to that treatment. The visit windows considered when defining what constitutes a missing value for hemoglobin level, spleen volume or MF SAF TSS is provided in [Section 2.1.1](#).

2.5.4 Supportive analyses (NOT applicable)

Sensitivity analyses (NOT applicable)

As sensitivity analyses, the primary endpoint in Parts 2 and 3, i.e. the response rate (RR) at the end of Cycle 6 (Section 2.5.1), will be evaluated with different prior distributions for the response rates:

1. The prior distribution for the response rate in the combination arm is the same prior as in the primary analysis, i.e., a vague prior. The prior distribution for the response rate in the ruxolitinib arm is the robustified MAP prior based on historical data from INCB18424-351 (Comfort I) and CINC424A2352 (Comfort II). The historical data from Comfort I and

Comfort II and the statistical methodological details and the summary of robustified MAP prior are described in [Section 5.5](#).

2. The prior distribution for the response rate in the combination arm is obtained by updating the vague prior, $beta(1/2, 1/2)$, using the number of responders from Part 1. Let i index the combination study arm, let n_{iP1} be the number of subjects of Part 1 arm i , and let r_{iP1} be the number of responders in Part 1 arm i . The updated prior distribution for the RR in the combination arm i is given by

$$beta \left(\frac{1}{2} + r_{iP1}, \frac{1}{2} + n_{iP1} - r_{iP1} \right)$$

The prior distribution for the responder rate in the ruxolitinib arm is not changed compared to the primary analysis.

For the two sensitivity analyses proposed above, the RR will be summarized using descriptive statistics (N, %) by treatment arm along with 95% creditable interval of the RR posterior distribution. The joint distribution of the posterior difference in response rates will be summarized using median and 95% credible interval. The probability that the posterior difference is greater than zero will also be presented.

Supportive analyses (NOT applicable)

As supportive analyses, the definition of 'responders' will be modified compared to the primary endpoint by only considering the hemoglobin and spleen volume measurement. Thus, for supportive analyses, a subject is considered a responder if the following two criteria are fulfilled:

- Anemia improvement is defined as an increase of hemoglobin from baseline of at least 1.5 g/dL at the end of 24 weeks after randomization. Anemia improvement requires absence of any PRBC transfusion in the 12 weeks prior to achieving an increase of 1.5 g/dL and a confirmation of Hb increase at least 2 weeks later.
- No spleen volume progression is given when the spleen volume increase is smaller than 25% between baseline and the end of Week 24 measured by MRI/CT.

Subjects with missing assessment of hemoglobin or spleen volume at the end of Week 24 that prevent the evaluation of the analysis endpoint will be considered as non-responders to that treatment.

The RR will be summarized using descriptive statistics (N, %) by treatment arm along with 95% creditable interval of the RR posterior distribution. The joint distribution of the posterior difference in response rates will be summarized using median and 95% credible interval. The probability that the posterior difference is greater than zero will also be presented.

2.6 Analysis of the key secondary objective

Not applicable

2.7 Analysis of secondary efficacy objective(s)

Due to the enrollment halt, some of the secondary efficacy objectives are no longer applicable. The updated secondary efficacy objectives are listed as follows:

- To evaluate changes in symptoms of myelofibrosis in each treatment arm using MFSAF v4.0 (Part 1 core)
- To evaluate the changes in spleen size (spleen volume and spleen length) in each treatment arm (Part 1 core and extension)

In final CSR, data collected in extension phase will be listed instead of summary tables.

2.7.1 Secondary endpoints

All secondary efficacy endpoints will be analyzed using the Full Analysis Set (FAS).

Proportion of subjects achieving improvement of hemoglobin level (NOT applicable)

Hemoglobin is measured at baseline and at least once per cycle. The change from baseline will be summarized by treatment group using descriptive statistics. Individual hemoglobin level at different time points will be displayed graphically by treatment group.

The proportion of subjects achieving improvement in hemoglobin ≥ 1.5 g/dL and ≥ 2.0 g/dL, respectively, from baseline to the end of Week 24, and the end of Week 48 will be summarized using descriptive statistics (N, %) by treatment arm along with two-sided exact binomial 95% CIs [[Clopper and Pearson 1934](#)]. The proportion will be calculated using FAS subjects as the denominator; the numerator will be based on the number of subjects with a baseline measure and a post-baseline measure of the corresponding time-point.

Change in spleen volume and spleen length

Spleen volume will be measured by MRI/CT at baseline, the end of every 24 weeks (8 cycles for NIS793 arms and 6 cycles for all other arms) and at EOT (if not performed in the past 12 weeks) for Part 1 core treatment phase and extension phase. The change from baseline will be summarized at each scheduled assessment time point by treatment group using descriptive statistics. The change from baseline at the end of Week 24 will be displayed graphically for individual subjects by treatment groups.

The proportion of patients with a spleen volume progression will be summarized using descriptive statistics (N, %) at the end of Week 24 and separately at the end of Week 48 by treatment group.

The proportion of subjects achieving at least 25% and 35% reduction in spleen volume from Baseline to the end of Cycle 8 (NIS793 arms) or Cycle 6 (all other arms) and the end of Cycle 16 (NIS793 arms) or Cycle 12 (all other arms) during the core treatment phase as measured by MRI or by CT will be summarized descriptively.

Spleen length measurement will be conducted by manual palpation. Manual palpation will be performed on days 1 and 15 of cycles 1 to 3, and day 1 of subsequent cycles for Part 1 core treatment phase and extension treatment phase. The change from baseline at each planned

scheduled point will be summarized by treatment group using descriptive statistics. The change from baseline at the end of Week 24 will be displayed graphically for individual subjects by treatment groups.

The proportion of subjects who achieved at least 50% spleen length reduction from baseline for subjects with baseline splenomegaly that is palpable at greater than 10 cm, or became not palpable for subjects with baseline splenomegaly that is palpable at $\geq 5\text{-}10$ cm will be calculated at the end of Cycle 4 (NIS793 arms) or Cycle 3 (all other arms), and at the end of Cycle 8 (NIS793 arms) or Cycle 6 (all other arms), and at the end of Cycle 16 (NIS793 arms) or Cycle 12 (all other arms).

Change in symptoms assessed by MFSAF and EORTC

Symptoms of myelofibrosis will be measured by MFSAF v4.0 and EORTC QLQ-C30 for the core treatment phase. Due to enrollment halt, EORTC data is not available for Parts 2 and 3 of the study.

MFSAF v4.0

MFSAF v4.0 ([Appendix 5.6](#)) is a harmonized, consensus-based PRO questionnaire recently developed for use in MF trials by a PRO Consortium Working Group ([Gwaltney et al 2017](#)), which focuses on the 7 core symptoms of MF: fatigue, night sweats, pruritus, abdominal discomfort, pain under the ribs on the left side, early satiety and bone pain.

Subjects record symptom severity at its worst for each of the 7 symptoms on an 11-point numeric rating scale, from 0 (absent) to 10 (worst imaginable). The 7-day recall format is used in this study. The Total Symptom Score (TSS) is calculated as the average of the observed individual item responses on the 0 to 10 scale multiplied by 7, resulting in a TSS ranging from 0 to 70. At least four items must be completed to calculate the TSS from the 7-day recall format of the MFSAF v4.0. MFSAF v4.0 is collected at Screening, C1D1, Day 1 of all subsequent cycles of treatment, as well as the EOT visit.

The change from baseline in MFSAF total symptom score and individual symptoms will be summarized with descriptive statistics by treatment group at each scheduled assessment time point for Part 1. The change from baseline at the end of Week 24 will be displayed graphically for individual subjects by treatment groups. The proportion of subjects with no worsening in symptom at the end of Week 24 and Week 48 will be summarized. The proportion will be calculated using FAS subjects as the denominator; the numerator will be based on the number of subjects with a baseline measure and a post-baseline measure of the corresponding time-point. The symptom worsening is defined as an increase in TSS of 10 or more from baseline.

The proportion of subjects who achieved at least 50% reduction in MFSAF v4.0 Total Symptom Score (TSS) at the end of Cycle 4 (NIS793 arms) or Cycle 3 (all other arms), at the end of Cycle 8 (NIS793 arms) or Cycle 6 (all other arms) and at the end of Cycle 16 (NIS793 arms) or Cycle 12 (all other arms) respectively from baseline will be calculated.

Progression free survival (PFS) (NOT applicable)

PFS is defined as the time from the date of randomization to the date of the first documented progressive splenomegaly, or accelerated phase, or deteriorating cytopenia, or leukemic transformation or death due to any cause. See Protocol Section 8.3.2.4 for the details of the PFS events definition. The PFS event and the corresponding date are taken from the Progressive Disease Assessment CRF page.

PFS will be analyzed using the FAS population according to the randomized treatment group assigned at randomization. The PFS distribution will be estimated using the Kaplan-Meier method, and the Kaplan-Meier curves, medians and 95% confidence intervals of the medians will be presented for each treatment group. The hazard ratio for PFS comparing a combination treatment with ruxolitinib single agent will be calculated, along with its 95% confidence interval, using a Cox model.

PFS will be censored if no PFS event is observed before the cut-off date or the date when a new anti-neoplastic therapy or another investigational treatment is started, whichever occurs earlier. The censoring date will be the date of last adequate assessment before a new anti-neoplastic therapy or another investigational treatment is started, if it occurred, else the date of last adequate assessment before the cut-off date.

Disease Progression

Disease progression will be assessed at every clinical visit. The date of assessment, date of confirmatory progressive disease, progressive disease criteria will be listed for core and extension treatment phases.

Proportion of subjects achieving improvement in bone marrow fibrosis (NOT applicable)

The grade of bone marrow fibrosis will be measured at baseline, the end of Week 24, and every subsequent 24 weeks. The grade of bone marrow fibrosis will be summarized descriptively for each scheduled point by treatment group. The proportion of patients achieving improvement in bone marrow fibrosis of ≥ 1 grade from baseline to the end of Week 24, and the end of Week 48 will be summarized by treatment group. The proportion will be calculated using FAS subjects as the denominator; the numerator will be based on the number of subjects with a baseline measure and a post-baseline measure of the corresponding time-point.

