In case of spleen length increase that meets any of the criteria for progressive spleen size as described below are met, an MRI/CT scan will be conducted to confirm spleen size progression.

- Appearance of a new splenomegaly that is palpable at least 5cm below the LCM, or
- A ≥ 100% increase in palpable distance, below LCM, for baseline splenomegaly of 5-10 cm, or
- A 50% increase in palpable distance, below LCM, for baseline splenomegaly of > 10 cm, as per IWG-MRT revised criteria (Tefferi et al 2013).

In case any of the criteria for progressive spleen size as described above are met, MRI/CT scan will be conducted to confirm spleen size progression.

Spleen volume assessment by MRI or CT scan

Assessment of spleen volume by MRI (or CT if MRI is contraindicated) will be performed as described in Section 8.3.1.2 at screening (baseline), at the end of Cycle 8 (arms with NIS793) or Cycle 6 (all other arms), then every 8 cycles (arms with NIS793) or 6 cycles (all other arms), and at EOT (if not performed in the past 12 weeks) as noted in Table 8-6. Previously completed scans can be considered for baseline if obtained within 8 weeks prior to first dose of study treatment.

During the extension treatment phase, assessment of spleen volume by MRI or CT scan should be performed as needed by investigator to assess subject spleen response and clinical benefit of study treatment.

Table 8-6 MRI/CT Assessment Collection Plan

Procedure	Timepoints
Abdomen MRI or CT	Screening/baseline (Day -28 to day-1)
	At the end of every 8 cycles for arms with NIS793 or 6 cycles for all other arms (± 7 days)
	EOT (if not performed in last 12 weeks)
	Treatment extension phase – as needed by investigator
	Unscheduled – at the discretion of investigator

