12.5.1.2 Change in spleen volume and spleen length

Spleen volume will be measured by MRI/CT at baseline, the end of Cycle 8 (NIS793 arms) or Cycle 6 (all other arms), the end of Cycle 16 (NIS793 arms) or Cycle 12 (all other arms) and at EOT (if not performed in the past 12 weeks) as noted in Table 8-6. The change from baseline will be summarized at each scheduled assessment time point during the core treatment phase using descriptive statistics.

The proportion of subjects with a spleen volume progression from baseline to the end of Cycle 8 (NIS793 arms) or Cycle 6 (all other arms) and the end of Cycle 16 (NIS793 arms) or Cycle 12 (all other arms) during the core treatment phase will be summarized descriptively. A spleen progression requires confirmation by MRI or CT showing a spleen volume increase of at least 25%.

The proportion of subjects achieving at least 25% and 35% reduction in spleen volume from Baseline to the end of Cycle 8 (NIS793 arms) or Cycle 6 (all other arms) and the end of Cycle 16 (NIS793 arms) or Cycle 12 (all other arms) during the core treatment phase as measured by MRI or by CT will be summarized descriptively.

Spleen length measurement will be conducted by manual palpation. Manual palpation will be performed on days 1 and 15 of cycles 1 to 3, and day 1 of subsequent cycles, as noted in the schedule of assessments in Table 8-3 and Table 8-5. The change from baseline at each planned scheduled point during the core treatment phase will be summarized using descriptive statistics.

The proportion of subjects who achieved at least 50% spleen length reduction at the end of Cycle 8 (NIS793 arms) or Cycle 6 (all other arms) from baseline during the core treatment phase for subjects with baseline splenomegaly that is palpable at greater than 10 cm, or became not palpable for subjects with baseline splenomegaly that is palpable at $\geq 5-\leq 10$ cm will be estimated.

The proportion of subjects who achieved at least 50% spleen length reduction at the end of Cycle 4 (NIS793 arms) or Cycle 3 (all other arms) from baseline during the core treatment phase for subjects with baseline splenomegaly that is palpable at greater than 10 cm, or became not palpable for subjects with baseline splenomegaly that is palpable at $\geq 5-\leq 10$ cm will be estimated.

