In addition, all AEs and SAEs which started during the overall safety period will be summarized.

A subject with multiple adverse events within a primary system organ class is only counted once towards the total of the primary system organ class.

All AEs, deaths and serious adverse events (including those from the pre, on-extension treatment period and post-treatment periods) will be listed and those started during the pre-treatment period, post-treatment period, and post-treatment/overall safety overlapping period will be flagged.

Vital signs

All vital signs data will be listed by treatment group, subject, and visit/time and if ranges are available, abnormalities (and relevant orthostatic changes) will be flagged. Summary statistics will be provided by treatment group for core treatment phase.

12-lead ECG

All ECG data will be listed by treatment group, subject and visit/time, abnormalities will be flagged. Summary statistics will be provided by treatment group for core treatment phase.

Clinical laboratory evaluations

All laboratory data will be listed by treatment group, subject, and visit/time and if normal ranges are available abnormalities will be flagged. Summary statistics will be provided by treatment and visit/time for core treatment phase. Shift tables using the low/normal/high/ (low and high) classification will be used to compare baseline to the worst on-treatment value for core treatment phase.

Grading of laboratory values will be assigned programmatically as per NCI Common Terminology Criteria for Adverse Events (CTCAE) version 5.0. The calculation of CTCAE grades will be based on the observed laboratory values only, clinical assessments will not be taken into account.

CTCAE Grade 0 will be assigned for all non-missing values not graded as 1 or higher. Grade 5 will not be used.

For laboratory tests where grades are not defined by CTCAE v5.0, results will be categorized as low/normal/high based on laboratory normal ranges.

The following summaries will be generated separately for hematology, and biochemistry tests:

5. Listing of all laboratory data with values flagged to show the corresponding CTCAE v5.0 grades if applicable and the classifications relative to the laboratory normal ranges

For laboratory tests where grades are defined by CTCAE v5.0:

- Worst post-baseline CTCAE grade (regardless of the baseline status). Each subject will be counted only once for the worst grade observed post-baseline.

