
• To characterize the pharmacokinetic profile of ruxolitinib administered in combination with sitemartin, crizanlizumab, sabatolimab, rinaterkib and NIS793, respectively (Part 1 core)• To assess emergence of anti-crizanlizumab, anti-sabatolimab, or anti-NIS793 antibodies following one or more IV infusions (Part 1 core)• To evaluate the changes in spleen size in each treatment arm (Part 1 core and extension)• To evaluate long-term safety and tolerability of ruxolitinib combination treatments in each arm (Part 1 core and extension)	
• Cycle 16 (NIS793 arms) or Cycle 12 (all other arms) from baseline.• PK parameters (e.g., AUC, Cmax, Tmax) and concentration vs. time profiles of each investigational drug with in combination regimens• Presence and/or concentration of anti-crizanlizumab, anti-sabatolimab or anti-NIS793 antibodies• Change in spleen length (by palpation) from baseline.• Change in spleen volume (by MRI/CT) from baseline, including proportions of subjects who achieved (i) at least 35% spleen volume reduction and (ii) at least 25% spleen volume reduction at the end of Cycle 8 (NIS793 arms) or Cycle 6 (all other arms, and at the end of Cycle 16 (NIS793 arms) or Cycle 12 (all other arms), or Cycle 21 (extension phase) from baseline respectively.• Frequency, duration and severity of adverse events, abnormalities in vital signs and laboratory test values, including ECG data

2 Statistical methods

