2.1 Data analysis general information

The data analysis (including analysis for DMC reviews, primary analysis, and final analysis) will be performed by Novartis personnel, Biostatistics and Statistical Programming departments. SAS version 9.4 or later and/or R version 3.0.2 or later will be used to perform all data analyses and to generate tables, figures and listings.

Data included in the analysis

At the time of protocol amendment version 08 release, all subjects have completed at least 8 cycles (arms with NIS793) or 6 cycles (all other arms) of treatment or discontinued earlier (Part 1 and Part 2). If the last core treatment phase subject entered extension treatment phase, the cut-off date for the primary analysis of study data will be established after the last subject performed the end of treatment visit (EOT) for core treatment phase (Part 1). If the last core treatment phase subject would not enter extension treatment phase, the cut-off date will be established after the last subject completed protocol defined safety follow up visit. All statistical analyses will be performed using all data collected in the database up to the data cut-off date. For clarification, Part 1 subjects might have entered extension treatment phase prior to the primary analysis cut-off date. In this case, extension treatment phase data prior to the cut-off date will also be included for the primary CSR. All data with an assessment date or event start date (e.g. vital sign assessment date or start date of an adverse event) prior to or on the cut-off date will be included in the analysis. Any data collected beyond the cut-off date will not be included in the analysis and will not be used for any derivations.

All events with start date before or on the cut-off date and end date after the cut-off date will be reported as 'ongoing'. The same rule will be applied to events starting before or on the cut-off date and not having documented end date. This approach applies, in particular, to adverse event and concomitant medication reports. For these events, the end date will not be imputed and therefore will not appear in the listings.

The final analysis for the extension phase data will be performed at the end of the study. The cut-off date for the final analysis of study data will be established when all subjects have completed the study. All extension treatment phase data will be reported in the final CSR.

General analysis conventions

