Safety summaries (tables, figures) include data from the pre-treatment period (to display the baseline status e.g. for ECG) and the on-treatment period, i.e. data from the post-treatment period with the exception of deaths should not be included unless requested from Health Authorities or external committees.

In particular, summary tables for adverse events (AEs) will summarize on-treatment events, with a start date during the on-treatment period, the so-called ***treatment-emergent*** AEs. Additionally, all (study treatment related/ regardless) AEs and SAEs with a start date during the overall safety period will be summarized.

However, all safety data (including those from the post-treatment period) will be listed and those collected during the pre-treatment, post-treatment overall safety period and post-treatment period are to be flagged.

For the final analysis, all extension treatment phase safety data will be listed and those collected during post-treatment overall safety period and post-treatment period are to be flagged. The safety data in part 1 core and extension phase will be summarized in tables for the extension treatment phase clinical trial safety disclosure.

Windows for multiple assessments

In order to summarize data collected over time (including unscheduled visits), the assessments will be time slotted. The following general rule will be applied in creating the assessment windows: If more than one assessment is done within the same time window, the assessment performed closest to the target date will be used. If two assessments within a time window are equidistant from the target date, then the assessment that occurred later will be used. If multiple assessments occur on the same date then the worst case will be used. Data from all assessments (scheduled and unscheduled), including multiple assessments, will be listed.

The following time windows are defined for descriptive summary on spleen imaging, spleen length palpation, ePROs, laboratory assessments [REDACTED] (Tables 2-1, 2-2, and 2-3) by visit regardless of core or extension treatment phases. The end of treatment assessment will be mapped into the time points as needed.

Table 2-1 Time windows for imaging assessments (MRI/CT of abdomen)

Time Point	Planned Visit Timing	Time Window Definition
Screening/Baseline	On or before Study Day 1*	≤ Study Day 1
Cycle 7 Day 1	Study Day 168	Study Days 140 – 196
Cycle 13 Day 1	Study Day 336	Study Days 308 – 364
Every 6 cycles thereafter		

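### The SAP assumes 24-weekly spleen scans in the extension and drops the protocol's core-only limit, so as-needed scans can enter by-visit spleen-volume summaries in the primary CSR (minor)

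*SAP*

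**What the plan says.** **Scan schedule.** SAP 2.7.1 gives one schedule for both phases: baseline, every 24 weeks, and "at EOT (if not performed in the past 12 weeks) for Part 1 core treatment phase and extension phase". Protocol 8.3.2.2 says that in the extension "assessment of spleen volume by MRI or CT scan should be performed as needed by investigator". Protocol Table 8-6 agrees. Table 8-2 has MRI/CT as clinically indicated from extension Cycle 2, with a scan at extension end of treatment (EOT) unless one was done in the previous 12 weeks.

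**Summaries.** Protocol 12.5.1.2 states: "The change from baseline will be summarized at each scheduled assessment time point during the core treatment phase using descriptive statistics". It puts the same core-phase limit on the proportion with spleen-volume progression. Protocol 12.5.2 says of laboratory data: "Summary statistics will be provided by treatment and visit/time for core treatment phase". SAP 2.7.1 (volume change and progression) and SAP 2.8.3 (laboratory) carry these summaries without the limit. SAP section 4 reports no change from the protocol analysis, and refers to amendment 8 although this SAP implements amendment 9.

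**Windows and data included.** SAP 2.1.1 builds visit windows for imaging and other assessments "by visit regardless of core or extension treatment phases", with unscheduled visits included. SAP 2.1 adds that, for subjects who entered the extension before the primary cut-off, "extension treatment phase data prior to the cut-off date will also be included for the primary CSR". SAP 2.7 says that extension efficacy data are listed rather than tabulated in the final CSR.

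**Cycle 21.** SAP Table 1-1 extends the 25% and 35% volume-reduction endpoint to "Cycle 21 (extension phase) from baseline respectively". Section 1.2 says that the table follows protocol Table 2-1, which stops at Cycle 12 (Cycle 16 for NIS793).

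**The concern.** A by-visit summary assumes that the scans in a row were taken because the visit came round. In the core phase that is largely so. In the extension, a scan before EOT exists because the investigator wanted one. Under protocol 8.3.2.2, a palpable increase that meets the stated criteria itself calls for a confirmatory scan. If such scans fill a row labelled Week 48, the change from baseline and the progression proportion partly reflect why the scan was ordered, and the table does not show it.

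With so few subjects, a late row in one treatment group may hold a single scan, so its origin matters to the reader. Section 4 would also tell that reader that nothing departs from the protocol.

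**Working it through.** **Inputs**
- Extension: at most 21 cycles, given as 84 weeks (protocol summary); 28-day cycles, since no NIS793 subject enters (protocol section 8).
- Imaging windows (SAP Table 2-1): centre 168 × m days, ± 28 days.
- Extension subjects: at most 4, on different combinations and/or dose levels (SAP 1.1).
- Individual core lengths: not given. Assumed values c (in cycles, minimum 6) are used, with dosing on schedule.

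**1. The plan's own figures.** 21 × 28 = 588 days = 84 weeks, as stated. For m = 1 and 2 the windows are 140–196 and 308–364 days, matching Table 2-1. Its formula then gives Cycle 19 at 476–532, Cycle 25 at 644–700 and Cycle 31 at 812–868.

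**2. Scans the SAP expects but the protocol does not schedule.** The extension runs from day 28c + 1 to day 28(c + 21).
- c = 6: days 169 to 756. The 24-week marks inside are days 336, 504 and 672, so 3.
- c = 9: days 253 to 756 + 84 = 840. The marks are days 336, 504, 672 and 840, so 4.

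The protocol makes all of these as needed.

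**3. Can an as-needed scan fill the Week 48 row?** A subject must be in the extension by day 364: 28c + 1 ≤ 364, so c ≤ 12 (c = 12 gives 337; c = 13 gives 365).
- c = 6 to 10: entry falls on days 169 to 281, and no core scan falls in 308–364. The row can be filled only by an as-needed scan, or by an EOT scan after early stopping.
- c = 11: entry and core EOT fall on day 309, which is 141 days after the day-168 scan, so an EOT scan is due. It lies 27 days from the target. SAP 2.1.1 takes the assessment nearest the target, so an as-needed scan on any of days 310 to 362 displaces it.
- c = 12: the scheduled scan falls at about day 336 and is normally kept.
- c ≥ 13: the window lies wholly within core.

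The route is open for core lengths of 6 to 11 cycles, provided that the scan precedes the primary cut-off. How many of the 4 subjects meet both conditions cannot be determined from the documents.

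**4. Where extension Cycle 21 would fall.** With c = 6 it ends on day 27 × 28 = 756, after the Cycle 25 window closes (700) and before Cycle 31 opens (812). The scan maps to no row. With c = 9 it ends on day 840, inside the Cycle 31 window. The time point therefore has no fixed place in the SAP's own windows.

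**5. Laboratory data.** In Table 8-2, hematology and chemistry stay scheduled at every extension cycle. Coagulation, urinalysis and thyroid tests were already as clinically indicated during core cycles. The missing core-only limit in SAP 2.8.3 is a departure from the protocol, but it does not newly mix routine with triggered measurements.

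**The case against.** The case against is that little reaches a table, and much of it stands. SAP 2.7 lists extension efficacy data in the final CSR. The primary cut-off follows the last subject's core EOT (or safety follow-up), so only subjects who crossed earlier contribute extension data. Core treatment continued past Cycle 6 with scans every 6 cycles, so late rows can also hold routine scans. Protocol 12.5.1.2 itself says that spleen data from both phases will be reported.

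A reader might also infer more than the documents support:
- **That extension scans are all triggered, so a Cycle 21 value must be.** An EOT scan is scheduled, and extension entry shares the core EOT visit. A completer's Cycle 21 value may be routine, although an as-needed scan in the preceding 12 weeks can stand in for it.
- **That the 25% and 35% response proportions are distorted.** SAP 2.7.1 already limits those to core, and no Cycle 21 proportion is specified there.
- **That laboratory, ECG or vital-sign summaries are biased.** Laboratory data are covered above. Scheduled ECGs were already only if clinically relevant after Cycle 6 in core for the two arms still on treatment. Vital signs are taken at every visit in both phases. SAP 2.8.4.1 and 2.8.4.2 count subjects with notable values, and neither data type is in the phase-blind windows.
- **That the protocol set the core-only limit because scanning changes.** It gives no reason.

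None of this removes the schedule mismatch, the dropped limit, or the open route into the primary CSR. The final-CSR listing rule does not govern that report.

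**Conclusion.** The point holds as a conflict between protocol and SAP, and within the SAP, and it is minor. The SAP states an extension scan schedule that the protocol does not have. It omits the core-only limit on by-visit spleen-volume change, spleen progression and by-visit laboratory summaries. It says that nothing changed, and it carries a Cycle 21 time point with neither source nor analysis.

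The practical exposure is the spleen-volume change rows and the Week 48 progression proportion in the primary CSR, from at most 4 subjects, in descriptive output with no test or decision attached. It depends on individual core lengths and on the cut-off date, which the documents do not give. No size of distortion can be stated, because nothing in the documents says how often as-needed scans occur or in whom.

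**What to change.** 1. SAP 2.7.1: describe extension scans as the protocol does, namely as needed, plus EOT if none in the previous 12 weeks.
2. SAP 2.7.1: restore the core-phase limit on the spleen-volume change and progression summaries. Restore it in SAP 2.8.3 for by-visit laboratory summaries, as protocol conformity. If a limit is left out on purpose, declare the departure in section 4. Update section 4 to refer to amendment 9.
3. SAP 2.1.1: limit the imaging windows used for summaries to core assessments.
4. SAP Table 1-1: remove extension Cycle 21, or mark it as listed only.
5. Flag each extension scan in the listings as unscheduled or EOT.

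The cost is SAP wording and one listing flag. Extension spleen values then appear in listings rather than tables, which SAP 2.7 already intends for the final CSR. If the primary CSR has already been issued, which the documents do not say, record the departure in section 4 and in the final CSR.
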